Acupuncture for Female Interstitial Cystitis/Painful Bladder Syndrome and Its Effect on the Urinary Microbiome: A Randomized Controlled Trial [name] [name], MS, [name]

> Version 4 11/09/2020

A. BACKGROUND AND CLINICAL SIGNIFICANCE:

Interstitial Cystitis/Painful Bladder Syndrome (IC/PBS), affecting nearly 7.9 million US adult women¹, is a complex chronic pelvic pain (CPP) condition characterized by suprapubic pain related to bladder filling and associated with urinary urgency and frequency in the absence of urinary infection or other obvious pathology². Quality of life with IC/PBS is significantly reduced particularly in those with concomitant pain comorbidities³. Proposed etiologies have included bladder glycsosaminoglycan (GAG) layer injury with resultant neurogenic inflammation, autoimmune basis with mast cell infiltration, epithelial dysfunction, infectious (⁴) and peripheral and/or central sensitization. The presentation of symptoms can be quite variable^{5,6}, suggesting that IC/PBS is a multi-factorial disease with overlapping etiologies⁷ driven by complex pelvic neural circuitry⁸. Definitive diagnostic criteria for IC/PBS and research measures that correlate with treatment outcomes are lacking⁴. Additionally, etiologic and contributing factors to symptom manifestation are not well defined.

Recent IC/PBS guidelines⁹ advocate first and second line treatment directed at pain management. Over 80% of patients with IC/PBS seek complementary and alternative medical (CAM) treatment¹⁰. There is mounting evidence to support acupuncture as an alternative therapy in various types of chronic pain¹¹. Several mechanisms of action have been proposed for acupuncture treatment effect. Various models have implicated cytokines, hormones (eg, cortisol and oxytocin), biomechanical effects, electromagnetic effects, the immune system, and the autonomic and somatic nervous systems (Andew C Ahn, Acupuncture. UpToDate). Current understanding of acupuncture's analgesic effect thought to be associated with neurotransmitters release at both the spinal and supraspinal levels. Recent preliminary evidence documents the efficacy of acupuncture in lower urinary tract symptom reduction in men with chronic prostatitis/CPPS¹². Yet there is a *significant knowledge gap* regarding its effect in women with IC/PBS.

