The Urinary Microbiota. Within internal surfaces, which are defined as existing outside the body (e.g. the intestinal epithelium or the vaginal epithelium), there exist commensal microbial communities. These microbiota are believed to be beneficial to human health, facilitating efficient removal of improperly functioning immune cells and protecting the host from pathogen infection¹³⁻¹⁵. The human bladder is a core component of the human urinary tract. It is a hollow muscular organ lined with transitional epithelium, which functions as the storage site for metabolic wastes in the form of urine. Given that the bladder's luminal space is also considered outside the body, it would seem reasonable that a urinary microbiota would be present. Yet, the historic doama has maintained that urine is "sterile," based on culture-dependent methods of bacterial detection. This paradigm is shifting, however, based on our newly published data noting the presence of a urinary microbiota in adult women without clinical urinary tract infections^{16,17}. Furthermore, we have recently discovered that the microbiota of women with overactive bladder (specifically with associated urgency incontinence) is distinguishable from the microbiota of women with stress urinary incontinence. These findings suggest that IC/PBS may be influenced by an alteration to the urinary microbiota. Indeed, recent evidence reports a difference in the urinary microbiome dominated by Lactobacillus in subjects with IC/PBS compared with healthy controls¹⁸. This work is limited by lack of correlative clinical symptomatology, small sample size and urinary samples that may have been contaminated.

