The reports that acupuncture's influence may be partially expressed through immune mechanisms are reinforced by the understanding that beta endorphin and met-enkephalin seem to be mediators between the central nervous system and immune system. The two substances have been shown to enhance natural killer cell activity and met-enkephalin increases in vitro T-lymphocyte rosette formation from human T-lymphocytes (Josef M. Helms. Acupuncture energetics **1995** | ISBN-10: **1572507063** | ISBN-13: **978-1572507067** | Edition: **1**st).

It seems logical to theorize that acupuncture treatment may lead to urinary microbiome change.

We propose that changes in bladder microbiota leading to this enhanced cytokine response may result in symptoms associated with IC/PBS and that acupuncture, by modulating cytokine response, in turn has effect on the urinary microbiome.

Our *long term goal* is to determine pelvic pain mechanisms that will inform clinically-relevant classification and evidence-based treatment of women with IC/PBS and CPP. *The short term goal* of this application is to determine the safety, tolerability and efficacy of acupuncture in women with IC/PBS as a neuromodulative treatment and to characterize the urinary microbiome before and after acupuncture treatment. Our approach will advance the understanding of the contribution and consequences of peripheral pelvic nociception in IC/PBS. Our *central hypothesis* is that women with IC/PBS will benefit from acupuncture compared with sham treatment and acupuncture will have an effect on the urinary microbiome.

This proposed work **impacts** public health with contributions of rigorous clinical and translational methods, suitable for future NIH clinical research networks, to evaluate and assess treatment outcomes in women with IC/PBS. It is likely that these methods will have impact beyond this group of affected patients, such as CPP related to irritable bowel syndrome, vulvodynia, pregnancy, and endometriosis.

B. INNOVATION: We believe that the proposed research is innovative, as current pharmacologic strategies for IC/PBS have limited success and/or problematic side effects, yet acupuncture has not been studied in this population to date despite its proven efficacy in other chronic pain disorders¹¹. In addition, no study to date has correlated the urinary microbiome in IC/PBS with clinical characteristics or with response to acupuncture treatment.

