D. DESIGN OVERVIEW: This prospective randomized single blinded study will compare the effect of true acupuncture compared with sham/minimal acupuncture in women with IC/PBS (n=30). Symptomatic IC/PBS participants will not be asked to stop taking standing medications such as neurological agents in order to participate in the study. All current medications will be recorded and will measured using the Medication Quantification Scale (MQS III)^{23,24}. They will be asked to refrain from use of short-acting opioids/acetaminophen/non-steroid anti-inflammatory medications during study visits. IC/PBS participants will engage in 7 acupuncture sessions once weekly. Initial visit would assess participant's response to needle insertion. Standard classical/true acupuncture treatment will be administered during 6 following visits to treatment group (n=15) and sham/minimal acupuncture will be administered to control group. Menstrual cycle time points will be recorded for each visit. Clean catch voided urine samples and vaginal swab will be obtained prior to initiation of intervention, on completion of intervention and 12 weeks post onset of study visits.

E. RESEARCH STRATEGY:

Specific Aim 1: To determine the safety and tolerability of acupuncture in women with IC/PBS.

Hypothesis 1: Acupuncture treatment (true and sham) will be safe and tolerable in women with IC/PBS.

Specific Aim 2: To determine if acupuncture is effective in reducing pain in women with IC/PBS compared to sham treatment.

Hypothesis 2: True acupuncture treatment will be effective in the treatment of pain in women with IC/PBS compared with sham/minimal treatment.

Specific Aim 3: To determine the association between acupuncture responders and the urinary microbiome.

Hypothesis 2: Acupuncture responders will exhibit change in the urinary microbiome compared with nonresponders after acupuncture treatment.

STUDY DESIGN/METHODS:

Acupuncture Component:

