Clinical Measurements:

The following clinical parameters will be assessed in all participants at baseline and repeated at follow-up 12 weeks after initiation of PFPT:

Demographics: age, self-reported race and ethnicity, vaginal parity, body mass index, menopausal and hormone replacement status, prior treatment for IC/PBS and other pelvic floor disorders, tobacco and alcohol use, prior medical and surgical history, medications including pain medications measured by the Medication quantification scale (MQS III)^{23,24}), allergy history, social history

Standardized physical exam: Abdominal exam with vaginal assessment of pelvic floor muscle function generalized muscle tenderness exam²⁵

Pain location, duration, intensity: Brief Pain Inventory – Short form (BPI-SF)²⁶, VAS pain scale²⁷, Short Form McGill Pain Questionnaire²⁸, Body Pain Diagram

Pain functional impact: Pain disability index²⁹; Patient Global Response Assessment (GRA)³⁰

Urinary/Pain Symptoms: Female Genitourinary Pain Index (FGuPI)³¹, Interstitial Cystitis Symptom Index and Problem Index (ICSI, ICPI)³²

Sexual Dysfunction: Female Sexual Function Index³³

Psychological impact/Coping style: Pain Catastrophizing Scale (PCS)³⁴, Beck Depression Inventory, second version (BDI-II)³⁵, Beck Anxiety Inventory (BAI)³⁶

Clean catch voided urine specimen: for urinalysis, culture and microbiome analysis

Vaginal Swab: to exclude vaginal bacteria from voided urine specimen.

Urinary Microbiome Approach:

In order to elucidate changes in the bladder's microbiota and to understand how the host's immune response may contribute to IC/PBS, we propose a multidisciplinary approach that blends molecular biology, immunology, genomics and clinical assessment. We will use *de novo* sequencing to determine the composition of the bacterial community present in the urine of women with IC/PBS undergoing acupuncture treatment. Urine will be collected at three time points via clean catch voided urine specimen and vaginal swab: at baseline, post intervention completion and 12 weeks after the onset of the intervention.

Preliminary Data: In April, 2012, we published data concluding that bacteria are present in the bladders of culture-negative women without symptoms of UTI¹⁶. More recently, we completed an analysis of 13 urine samples from individual women with either stress urinary incontinence (SUI) or urgency/frequency (U/F) or both.

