From this preliminary analysis, we found that the urine microbiota differs between patients with predominately SUI symptoms compared to those with predominately U/F symptoms. *Figure 1* shows the illustrative results of our microbiota analysis of these 13 samples. The composition of the microbiota for each patient was determined by sequencing 150 nucleotides of the DNA encoding for the RNA molecule found within the small unit of the bacterial ribosome. These sequences identify the bacterial species present in each patient's urine. Principle component analysis (PCA) was used to determine the amount of difference between the groups of patients. This graph depicts the result of this examination, which suggests the microbiota of women with SUI or SUI>U/F significantly differ from that of women with U/F or U/F>SUI. This difference has the potential to be used as biomarker for various types of bladder dysfunction. Our results clearly indicate that the urine microbiota may be related to the etiology of different UI subgroups. Subsequently, we hypothesize that measurable biological changes in the urinary microbiota and/or urinary cytokine levels correlate with irritative bladder symptoms in women with IC/PBS.

[figure not shown]

Figure. 1: PCA- patients of different UI subgroups can be distinguished by their microbiota. SUI (orange) and SUI >U/F (lime) are different than U/F (aqua) and U/F >SUI (blue) along Axis 2.

Analysis of Urinary Bacterial Communities by De Novo Whole Genome DNA Sequencing (WGS) Rationale. Most microbiome studies define a catalog of bacterial species present in the microbial community on the basis of the sequence of one or more variable regions of the 16S ribosomal RNA (16S rRNA) gene. This assay is based upon a similarity between what is present in the sample and what bacterial species are already known. Therefore, many bacterial species present in the community may not be identified. *De novo* whole genome sequencing eliminates this bias. Genome assembly is based upon the presence of overlapping sequence between the assayed DNA fragments. Thus, the entire bacterial community can be identified, exponentially increasing our understanding of the relationship between the bladder's bacterial community and

OAB. The rapidly decreasing cost of WGS makes this more comprehensive approach feasible and thus desirable.

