The primary objective is to compare the mean BPI-SF worst pain score at following acupuncture between groups. All other analyses are secondary outcomes. A separate linear mixed effects model will regress each pain score outcome on group (minimal versus electro-acupuncture), time (baseline, end of treatment, or end of follow-up), and a group by time interaction. Random intercepts will be included to account for within-patient correlation. Adjusted means and standard errors will be estimated, and main effects and the group by time interaction will be formally tested within the mixed model. A similar linear mixed effects model will regress relative abundance of uropathogen on group, time, and the group by time interaction. Based on the prior work of Crew KD et al.³⁷, a sample size of 30 participants (15 per arm) was calculated to yield 90% power to detect a reduction of 2.5 on the BPI-SF worst pain item at a 5% significance level, assuming a standard deviation of difference in score between treatment groups of 2.5 points. This includes a dropout rate of 10% A reduction of at least 2 points on the BPI-SF worst pain item is considered to be a clinically meaningful decrease based on the literature³⁸. All statistical analyses will be two-sided and performed using SAS 9.4 (SAS Institute, Cary, NC).

G. FUTURE DIRECTIONS: The impact and potential benefits of identifying new nonpharmacologic treatment in women with IC/PBS will be critical to reduce disease severity and improve quality of life across female IC/PBS and all CPP subtypes. These same methods will be employed for future clinical trials in IC/PBS and other CPP subtypes. In future studies, participants could be reassessed monthly for 6 months after post-intervention assessment (6 months after completing the treatment protocol), and subjects who relapse could receive one to two booster/maintenance acupuncture sessions with additional studies performed on the urinary microbiome.

H. TIMELINE:

Research Activity	Year 1 (2013 – 2014)			
	Qt 1	Qt 2	Qt 3	Qt 4
Recruitment and Evaluation of Participants	Х	Х	Х	
Data Collection	Х	Х	Х	
Data Analysis/Manuscript writing/editing			Х	Х

REFERENCES CITED:

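### Section F measures the microbiome only as one undefined uropathogen proportion, so a change elsewhere in the urinary community could be reported as no microbiome effect

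*Combined protocol and SAP*

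**What the plan says.** **The question.** Section A closes with the central hypothesis, part of which is that "acupuncture will have an effect on the urinary microbiome". Section E, Specific Aim 3, reads "To determine the association between acupuncture responders and the urinary microbiome", and the hypothesis under it is that "Acupuncture responders will exhibit change in the urinary microbiome compared with nonresponders after acupuncture treatment". All three refer to the microbiome as a whole.

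**The measurement.** The Urinary Microbiome Approach sets out to "determine the composition of the bacterial community present in the urine of women with IC/PBS". Its sequencing rationale prefers whole-genome sequencing to 16S and concludes: "Thus, the entire bacterial community can be identified". The preliminary data in the same part separate patient groups by principal component analysis of whole communities. The one IC/PBS microbiome finding cited in section A is that "recent evidence reports a difference in the urinary microbiome dominated by Lactobacillus in subjects with IC/PBS compared with healthy controls".

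**The analysis.** Section F gives one sentence: "A similar linear mixed effects model will regress relative abundance of uropathogen on group, time, and the group by time interaction". It lists no taxa and sets no threshold for uropathogen. Section C also announces a microbiome comparison with 20 control women, but section F gives no variable or method for it.

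**The concern.** The variable in section F is much narrower than the question. It records how much of the community is uropathogen and ignores how the rest is arranged. If acupuncture altered Lactobacillus dominance or diversity while the uropathogen share stayed put, an analyst following section F would report no microbiome effect, although the sequence data held one. Because the taxa are not listed, two analysts could also compute different values from the same reads.

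A second worry is conditional. IC/PBS is defined in section A as occurring "in the absence of urinary infection or other obvious pathology". If uropathogen shares are therefore low in most women, the variable has little room to fall, and a linear model on a bounded proportion with many zeros would behave poorly.

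**Working it through.** **Plan's own figure.** There is none for the microbiome. The only sizing statement in section F (15 per arm, 90% power) concerns BPI-SF worst pain and is not used here beyond the arm size.

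**Step 1: can the community move while the variable does not?** This needs no abundance figure from outside. Take a community of two non-uropathogen taxa plus a uropathogen share u.

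- Before: 0.9(1 − u), 0.1(1 − u), u
- After: 0.1(1 − u), 0.9(1 − u), u

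For proportions, Bray-Curtis dissimilarity = 1 − Σ min(before, after) = 1 − [0.1(1 − u) + 0.1(1 − u) + u] = 0.8(1 − u).

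| Uropathogen share u | Bray-Curtis | Change in planned variable |
|---|---|---|
| 0% | 0.80 | 0 |
| 2% | 0.78 | 0 |
| 10% | 0.72 | 0 |
| 30% | 0.56 | 0 |
| 50% | 0.40 | 0 |

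The zeros follow because u is held fixed by construction. The table shows what can be missed, at any uropathogen level. It does not show what will happen.

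**Step 2: is there a floor?** The documents give no baseline, expected or preliminary uropathogen abundance, so every input here is assumed.

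- Arm size: 15, or 13 after the stated 10% dropout (15 × 0.9 = 13.5, rounded down).
- Carriers: 10% to 90% of women, with a mean share of 2% to 30% among carriers (beta distribution, precision 4) and zero in the rest.
- Active arm: loses all uropathogen.
- Sham arm: a carrier's follow-up value is 80% of her baseline plus 20% of a fresh draw from the whole distribution, zeros included.
- Test: two-sided t-test on change at the 5% level, 4,000 simulated trials. This is simpler than the planned three-visit mixed model.

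| Carriers | Mean share in carriers | Overall mean (product) | Power, 13 / 15 per arm |
|---|---|---|---|
| 10% | 2% | 0.2% | 0.0% / 0.0% |
| 10% | 10% | 1% | 0.2% / 0.2% |
| 20% | 30% | 6% | 7.6% / 8.7% |
| 40% | 30% | 12% | 40.3% / 49.0% |
| 60% | 30% | 18% | 80.9% / 87.3% |
| 90% | 10% | 9% | 73.0% / 83.7% |
| 90% | 30% | 27% | above 99% / above 99% |

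Power to detect complete clearance runs from practically nil to practically certain over the assumed range. The floor is severe if shares are near zero and absent if they are not. The documents do not say which applies.

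**The case against.** **A stronger reading a reader might infer** is that the uropathogen share must sit near zero in women without urinary infection, so the endpoint is uninformative. The documents do not support it. They give no abundance, and uropathogen is undefined. The preliminary data stress that sequencing finds bacteria where culture and symptoms do not, so the absence of clinical infection does not fix a sequencing-based share. Section C requires no negative culture at entry, and its UTI item stands in the exclusion list in negative form. Read literally, that item conflicts with the disease definition in section A; the two need reconciling, and the item cannot carry the argument. A floor also limits only decreases.

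**Relative abundances sum to one.** If Lactobacillus moves, other shares must move. The uropathogen share stays fixed only when other non-uropathogens absorb the whole shift. This stands: a community change *could* leave the variable unchanged, but need not.

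**A uropathogen measure has a rationale.** The Cytokines and Pain part of section A builds a pathogen-driven mechanism. This stands, and is a reason to keep the variable. The Lactobacillus observation is a cross-sectional comparison that the protocol itself calls limited. It makes Lactobacillus worth measuring but does not predict a treatment effect on it.

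**Community measures on voided urine carry vaginal bacteria.** This stands, and the fix must deal with it.

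**This is a secondary outcome in a pilot, and the sequences can be explored later.** True, and it limits the weight of the point. But a community measure chosen after the data are seen would not be a prespecified test of the stated hypothesis.

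**Conclusion.** Section F contains no prespecified analysis of community change, although the central hypothesis and Aim 3 ask about it and the sequencing is chosen to observe it. That conclusion rests on the text alone. Its possible size is shown by Step 1: a dissimilarity of up to 0.80 with no movement in the planned variable, given a shift confined to non-uropathogen taxa. The floor is a plausible additional weakness that the documents neither establish nor rule out. The primary pain comparison is unaffected. This is an inexpensive improvement to a secondary analysis that should be made before the microbiome data are analysed.

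**What to change.** In section F:

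1. List the taxa counted as uropathogen, and keep the planned model for that share.
2. Add Lactobacillus relative abundance (log-ratio or logit scale) and Shannon diversity as secondary outcomes in the same group-by-time mixed model.
3. Add each woman's Bray-Curtis distance from her own baseline, compared between groups at end of treatment and at week 12 only. This measure has no baseline value and cannot enter the three-visit model.
4. State how the vaginal swab data are used to remove vaginal bacteria before these measures are computed. The Sequencing Approach describes DNA from urine only, so say what swab data will exist. Control women give no swab, so a swab-based rule can serve only the randomised comparison.

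**Cost.** The same urine specimens and sequence data are used, with a few more secondary measures and tests, which should be labelled as such. If the swabs are not already to be sequenced or otherwise typed, item 4 needs more than a wording change.

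**Not repaired.** Aim 3 contrasts responders with nonresponders, whereas section F compares randomised groups and defines no responder. That gap needs its own correction.

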This is a randomized, controlled, single-blinded, pilot trial to study the feasibility, safety, and efficacy of acupuncture in IC/PBS women. Women will be recruited from the patient population of the Loyola University Medical Center who meet criteria for diagnosis of IC/PBS. This trial had 2 arms comparing the treatment of IC/PBS symptoms with acupuncture or sham/minimal acupuncture (placebo). Thirty (30) patients with IC/PBS will be enrolled as study participants into the study. Fifteen (15) will be allocated in the treatment classical acupuncture + medical management of IC and fifteen (15) will be allocated in the control sham/minimal acupuncture + standard medical treatments of IC. The acupuncturist will interview each patient and perform an exam. A standardized acupuncture treatment will be assigned, and both groups will receive 7 acupuncture treatments that follow a standardized protocol on classical acupuncture points, with or without mild electrical stimulation versus sham/minimal acupuncture. Acupuncture needles are single use, sterile and disposable. Standard acupuncture treatment protocol will include 4 gates plus GV 20 to reduce anxiety and help with relaxation and to assess acupuncture naïve patient's response to needles during their first acupuncture encounter. Subsequent visits would include administration of curious meridian Chong Mo paired with Yang Ming. 4 Hz low level electrical stimulation will be applied. Control group will receive sham/minimal acupuncture with low level electrical stimulation. The sham intervention (also described as minimal intervention) will use superficial needle insertion at body locations not recognized as true acupoints. Patients will be explained that various acupuncture treatment protocols will be tested including "minimal acupuncture", therefore, the control group will not be aware of receiving sham acupuncture. These described acupuncture treatments are well accepted treatment protocols for women with pelvic pain and bladder complaints.

Acupuncture or sham needle treatments will be performed once a week for 7 weeks. All subjects will be reassessed following the 7-week intervention phase and then 12 weeks from initiation of study. All subjects will be treated by single acupuncture practitioner ([name]) who is also a board certified urologist specializing in IC/PPS and is a current associate member of American Academy of Medical Acupuncture and board eligible for the American Board of Medical Acupuncture.

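### The stated 90% power does not follow for the between-arm comparison: about 70–75% if the 2.5-point SD is within-arm, about 94–96% if it is the SD of a treated-minus-control difference

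*Combined protocol and SAP*

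**What the plan says.** Section F (Data Analysis/Sample Size Estimation) sets the primary objective: "The primary objective is to compare the mean BPI-SF worst pain score at following acupuncture between groups". Hypothesis 2 in section E is likewise a comparison of arms: "True acupuncture treatment will be effective in the treatment of pain in women with IC/PBS compared with sham/minimal treatment". Section E allocates 15 patients to each of two parallel arms.

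The power statement in section F reads "a sample size of 30 participants (15 per arm) was calculated to yield 90% power to detect a reduction of 2.5 on the BPI-SF" (its item for worst pain). It sets the level at 5% and describes the SD thus: "assuming a standard deviation of difference in score between treatment groups of 2.5 points". It adds "This includes a dropout rate of 10" per cent, so about 27 of the 30 patients are expected to be evaluable. The section also says "All statistical analyses will be two-sided". The analysis is a linear mixed model with group, time and their interaction: "Random intercepts will be included to account for within-patient correlation". No value is given for that correlation, no test is named for the power calculation, and the inputs are attributed to an earlier sham-controlled acupuncture trial.

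**The concern.** Three things in the power statement are left open: whether the 2.5-point reduction is a between-arm difference, which test was used, and what the SD describes. In a parallel-arm trial no patient has a treated-minus-control difference of her own, so the printed label can be read in two ways:

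- **Reading A:** 2.5 is the SD within each arm, of either the score or its change from baseline.
- **Reading B:** 2.5 is the SD of the difference between one treated and one control patient. This is closer to the printed words.

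This statement is the only justification given for 30 patients. Against a stated 10% risk of missing a 2.5-point effect, the risk would be 25–30% on reading A and about 4–6% on reading B. A reader facing a non-significant result needs to know which of these applies.

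**Working it through.** **Inputs (all from section F).** Difference 2.5 points; SD 2.5; two-sided 5%; 15 per arm enrolled; 10% dropout included, so 0.9 × 30 = 27 evaluable, taken as 14 and 13.

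**Reproducing the printed figure.** A one-sample or paired t-test with difference/SD = 2.5/2.5 = 1 has noncentrality √n. Power is 88.3% at n = 12 and 91.1% at n = 13, so 13 are needed. Allowing for dropout, 13/0.9 = 14.4, rounded up to 15. This matches the printed size, but the formula is for one sample or matched pairs. Whether it was the one used cannot be shown from the documents.

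**The planned comparison.** For a two-sample t-test with n₁ + n₂ − 2 degrees of freedom, the noncentrality is 2.5 / [SD × √(1/n₁ + 1/n₂)].

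- Reading A, 15/15: standard error 2.5 × √(2/15) = 0.913; noncentrality 2.74; power 75.3%.
- Reading A, 14/13: standard error 0.963; noncentrality 2.60; power 70.4%.
- Reading B: within-arm SD 2.5/√2 = 1.77.
- Reading B, 15/15: standard error 0.645; noncentrality 3.87; power 96.2%.
- Reading B, 14/13: standard error 0.681; noncentrality 3.67; power 94.1%.

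| | Reading A (within-arm SD 2.5) | Reading B (within-arm SD 1.77) |
|---|---|---|
| Power, 15/15 | 75.3% | 96.2% |
| Power, 14/13 | 70.4% | 94.1% |
| Power, 13/13 | 68.7% | 93.3% |
| Evaluable per arm for 90% | 23 (22 gives 89.97%) | 12 (11 gives 88.4%) |
| Enrolled per arm at 10% dropout | 23/0.9, rounded up to 26 | 12/0.9, rounded up to 14 |
| Detectable difference, 14/13, at 80% / 90% power | 2.81 / 3.25 points | 1.98 / 2.30 points |
| Expected 95% CI half-width, 14/13 | 1.98 points | 1.40 points |

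The within-arm SD that gives exactly 90% is 2.04 (15/15) or 1.92 (14/13), which is neither 2.5 nor 1.77.

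**Other routes to 90%.** Results are for 15/15, then 14/13.

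- Normal approximation: A 78.2%, 73.8%; B 97.2%, 95.7%.
- One-sided 5%, contrary to the plan: A 84.8%, 81.1%; B 98.4%, 97.3%.

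**Could the repeated measures recover it on reading A?** This needs assumptions that the plan does not state: a raw-score SD of 2.5, complete data, and the same correlation r between all visits, varied from 0.3 to 0.7.

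- Change contrast from the planned model, SD 2.5 × √[2(1 − r)], with 2(N − 2) degrees of freedom: power 62.4–93.5% (15/15) or 57.6–90.8% (14/13). It reaches 90% at r = 0.66 and 0.69.
- Baseline as a covariate, SD 2.5 × √(1 − r²), with N − 3 degrees of freedom: power 79.0–95.9% or 74.3–93.7%. It reaches 90% at r = 0.58 and 0.64.

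If 2.5 is already the SD of change scores, the change contrast has the reading A power, and these correlation thresholds do not apply.

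**The case against.** The best defence is that no shortfall has been demonstrated. Reading B is nearer the printed label, and on it 28 enrolled patients would be enough, so 30 exceeds the need and 90% is slightly modest. The earlier trial that supplied the inputs would settle the matter, and it is not in the documents. That stands: the direction of the error cannot be established, and underpowering cannot be asserted outright.

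A second argument is that the planned mixed model uses baseline and follow-up data, and some correlations between 0.3 and 0.7 do bring the between-arm test to 90%. Also, patients who drop out may still contribute partial data, so 27 complete cases may be a little pessimistic. Both are true in principle. But the plan states no correlation, and at r = 0.3 the change contrast has less power than the plain two-sample test. An unstated input cannot be credited.

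Third, this is a pilot, and only a sentence would change. A pilot may reasonably have 70% power. However, this one lists efficacy among its aims and makes a formal 90% claim, which should follow from its own inputs.

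**Conclusion.** The concern holds. Applied to the two-sided between-arm comparison, the printed inputs give 70.4–75.3% power if 2.5 is the within-arm SD, and 94.1–96.2% if it is the SD of a treated-minus-control difference (lower figure after 10% dropout, upper figure with all 30 evaluable). Neither is 90%. These figures rest on an unadjusted two-sample t-test with equal SDs in the arms and no contribution from dropouts.

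The mismatch itself is certain; its direction is not. On reading A the trial falls 15–20 percentage points short of its claim, and the expected confidence interval of about ±2.0 points is as wide on each side as the 2-point reduction that section F treats as clinically meaningful. A null result could then be over-read. On reading B the sample is adequate, and only the label and the figure need correcting.

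**What to change.** Keep the 30 patients and the planned model. In section F, say which SD 2.5 is (within-arm score, within-arm change, or treated-minus-control difference), state that 2.5 points is a between-arm difference, and name the primary contrast and time point. Then restate power, using whichever wording applies:

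- *Within-arm:* With 30 enrolled and 10% dropout (27 evaluable), a two-sided 5% two-sample test has about 70% power for a 2.5-point between-group difference with a within-arm SD of 2.5; the detectable difference is 2.8 points at 80% power and 3.25 at 90%.
- *Treated-minus-control difference:* With a within-arm SD of 1.77 and 27 evaluable, the same test has about 94% power for a 2.5-point between-group difference.

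If credit is taken for baseline data, state the contrast and the assumed correlation. Report the primary between-group difference with a 95% confidence interval.

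The cost is wording only. The restated figure is less favourable than 90% in the first case and more favourable in the second.
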